8.6. COLUMBIA-SUICIDE SEVERITY RATING SCALE (C-SSRS)

The C-SSRS¹³ is an assessment tool used to assess the lifetime suicidality of a subject (C-SSRS at baseline) as well as any new instances of suicidality (C-SSRS since last visit).

8.7. ZARIT BURDEN INTERVIEW (ZBI)

The ZBI^{14,15} is a 22-item scale designed to assess the stress or burden experienced by caregivers of people with dementia. The ZBI will be administered as an interview with the caregiver. The scale consists of 22 statements reflecting how people can feel when taking care of another person. The statements are phrased as questions for the caregiver to indicate how often they feel the way described in the statement. The 5 possible responses for each item are Never, Rarely, Sometimes, Quite Frequently, and Nearly Always.

8.8. GERIATRIC DEPRESSION SCALE (GDS)

The GDS¹⁶ is a 30-item yes/no question test designed to screen for depression in elderly persons. The GDS short form (15-items)¹⁷ version utilized in this study will be clinician administered with caregiver input. Subjects will be evaluated for symptoms of depression during the Screening Period. The GDS scale score should be clinically interpreted to evaluate the potential for a major depressive episode by a clinician who has been trained on the scale and is familiar with the diagnosis of major depression.

8.9. ELECTRONIC CAPTURE OF RATING SCALES

The assessments MMSE, CDR, ADAS-Cog12, GDS, NPI, ADCS-ADL, C-SSRS, and ZBI will be captured electronically by an eCOA platform that is 21 CFR Part 11 compliant. Data collected by eCOA will be transferred directly to the EDC vendor's Page 39 of 52 CONFIDENTIAL

database.

The electronic capture of the rating scales will include an audio recording for the purpose of monitoring site staff performance during scale questionnaire administration and providing constructive feedback to the raters. Subject data captured on recordings will not be analyzed as part of the trial outcomes. The Investigator or rater will read the questions out loud to study participants who will then respond. The process of questions and answers will be recorded using an audio-recording device. These highly secured recordings will not be made public at any time and will be destroyed after the Study Drug has been either approved or disapproved for use by the FDA or other pertinent regulatory bodies.

9. EARLY DISCONTINUATION

Subjects may choose to discontinue Study Drug or study participation at any time, for any reason, and without prejudice. Moreover, a subject may be withdrawn at any time at the discretion of the Investigator or Sponsor for safety, behavioral or administrative reasons. Discontinued subjects should be followed according to medical practice standards, and the outcome documented. Follow-up is required if the subject is discontinued due to an adverse event (AE). Any comments (spontaneous or elicited) or complaints made by the subject and the reason for termination and the date of stopping the drug must be recorded in the Case Report Form (CRF) and source documents.

The following must be completed and documented in the source documents and CRFs for all subjects who discontinue the study early:

- The reason for early study discontinuation. If the subject is withdrawn for more than one reason, each reason should be documented in the source documents and the most clinically relevant reason should be entered on the CRF.
- •Vital signs (blood pressure, temperature and pulse), brief physical and neurologic examination, weight, clinical laboratory tests, 12-lead resting ECG (5 min supine), use of concomitant medications and adverse events should be obtained at discharge prior to release.
- •Blood draw for plasma biomarkers
- •ADAS-Cog12, MMSE, CDR, ADCS-ADL, NPI, ZBI and C-SSRS (as detailed in Section 7.1.6 Early Termination Visit), if not performed within the last 30 days.

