7.1. EVALUATIONS BY VISIT

Follow-up visits can be scheduled +/- five (5) days from the targeted Study Visit date.

7.1.1. Screening Period (No greater than a 60-day duration prior to Study Day 1)

The Sponsor recognizes the Screening Period assessments and procedures may not necessarily be completed in a single visit. A subject is permitted to be screened over more than one calendar day if, in the Investigator's judgment, such scheduling will optimize the accuracy of Screening Period assessments and procedures. The following will be completed during the Screening Period:

- Informed Consent.
- Review of Inclusion and Exclusion Criteria
- Collect demographic information (e.g., sex, date of birth, race/ethnicity, level of education)
- Medical and surgical history
- Review concomitant medications and any recently discontinued medications.
- To the extent such information is available, review and record any investigational drugs administered during past clinical study participation regardless of the date of such participation.

- History of drug, alcohol and tobacco use
- eCOA order of administration at screening:
 - o Note it is a study requirement to first administer the MMSE (and then the other assessments if the MMSE criterion is met)
 - MMSE
 - CDR (study partner is interviewed first in the absence of the study subject and then the subject is interviewed, by the same rater, in the absence of the study partner)
 - Geriatric Depression Scale
 - C-SSRS Baseline/screening version
- Complete physical and neurologic examination; including measurement of key vital signs (blood pressure [supine], temperature, pulse rate), height and weight (to calculate BMI)
- A 12-lead resting ECG (5-min supine)
- Laboratory assessments, including routine serum chemistry, TSH, free T4, Vitamin B12 levels, HBsAg, HCV-Ab, hematology, urinalysis and urine screen for drugs of abuse. Plasma for P-tau181 or P-tau217 assessment will also be collected unless there is documented evidence of AD pathophysiology prior to screening. For subjects with diabetes, collect a blood sample for HbA1C. Unexpected, abnormal laboratory results observed during the Screening Period should be captured as Medical History and not as an AE (see Section 10.1 Adverse Events Definition).

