7.1.6. Week 52 End-of-Treatment Visit / Early Termination (ET) Visit

Subjects will return to clinic for this scheduled visit within $a \pm 5$ -day "window." Subjects in the PK and plasma biomarker sub-study should **not** take an a.m. dose prior to their blood draw.

- Vital signs (blood pressure [supine], temperature and pulse)
- Weight
- Brief physical and neurologic examination
- Adverse Event monitoring

- Use of concomitant medications
- eCOA order of administration:
 - Note it is acceptable to simultaneously administer the study partner assessments in parallel with subject assessments (separate, qualified raters in separate rooms except for CDR). When administered in parallel, the eCOA order of administration should be maintained (ADAS-cog12 and then MMSE for the subject, and ADCS-ADL, for the study partner; for the CDR, the study partner is interviewed first in the absence of the study subject and then the subject is interviewed, by the same rater, in the absence of the study partner; the C-SSRS is then administered to the subject, and the NPI and ZBI are then administered to the study partner).
 - ADAS-Cog12 (whenever possible, within 1 hour of the time of day administered at the Baseline Visit [Study Day 1], and by the same rater)
 - ADCS-ADL
 - MMSE
 - CDR
 - NPI
 - ZBI
 - C-SSRS Since Last Visit version
- Clinical laboratory tests (blood and urine)
- For those 100 subjects participating in the PK and Plasma Biomarker sub-study, collect their Week 52 blood samples.
- A 12-lead resting ECG (5 min supine)

Note: Early Termination subjects do not need to complete the eCOA if performed within 30 days of the ET Visit (see Section 9 – Early Discontinuation)

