16. APPENDIX A – SCHEDULE OF ACTIVITIES

Procedures	Screening Period (-60 Days to 0)	Baseline Visit (Study Day 1)	Week 4	Week 16	Week 28	Week 40	Week 52 ET/ED ³	Safety Follow- up ⁸
Informed Consent	X							
I/E Criteria	X	X						
Medical & Surgical History	X							
Adverse Events	X	X	X	X	X	X	X	X
Concomitant Meds	X	X	X	X	X	X	X	
Vital signs	X	X	X	X	X	X	X	
Physical Examination	X ¹	X	X	X	X	X	X	
Neurologic Examination	X ¹	X	X	X	X	X	X	
Height	X							
Weight	X	X	X	X	X	X	X	
Resting ECG	X	X ⁹	X		X		X	
Biochemistry, Hematology, Urinalysis	X	X	X	X	X	X	X	
Urine Drug Screen	X							
TSH, free T4, B12, HBsAg, HCV-Ab	X							
HbA1c (diabetic subjects only)	X							
Plasma P-tau181 or P-tau217	X ⁷							
Genotyping sample		X						
MRI	X							
PK and Plasma Biomarkers	X ²				X ²		X^2	
MMSE	X				X		X	
CDR	X						X	
Geriatric Depression Scale	X							
ADAS-Cog12		X	X	X	X	X	X	
ADCS-ADL		X	X	X	X	X	X	

Procedures	Screening Period (-60 Days to 0)	Baseline Visit (Study Day 1)	Week 4	Week 16	Week 28	Week 40	Week 52 ET/ED ³	Safety Follow- up ⁸
NPI		X			X		X	
ZBI		X	X	X	X	X	X	
C-SSRS	X ⁴	X ⁵	X ⁵	X ⁵	X ⁵	X ⁵	X ⁵	
Drug Dispensation		X^6	X	X	X^6	X		
Drug Accountability			X	X	X	X	X	
End of Study Follow-up Phone Call								X

- 1. Complete Physical and Neurologic Examinations during the Screening Period only, brief examinations thereafter
- 2. PK and plasma biomarker sub-study subjects only (100 subjects total; 50 subjects/group)
- 3. Early Termination / Early Discontinuation subjects do not need to complete the electronic clinical outcome assessments if performed within 30 days of the ET/ED Visit
- 4. During the Screening Period, the C-SSRS Baseline/Screening version will be administered
- 5. At Study Day 1, as well as all remaining visits, the C-SSRS Since Last Visit version will be administered
- 6. The first dose of Study Drug is administered at the clinic to all subjects on Study Day 1; for plasma PK and biomarker sub-study subjects only at the Week 28 visit, administer Study Drug after blood samples are collected
- 7. Plasma P-tau181 or plasma P-tau217 not required if the subject has evidence for AD pathophysiology prior to screening
- 8. This phone call will occur Week 53 to 54 for those subjects who complete all study visits, or 1 to 2 weeks after Early Termination. If the subject reports an adverse event, the subject should be followed and treated by the Investigator until the AE has resolved or stabilized.
- 9. ECG on Study Day 1 collected in triplicate

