2.7. Schedule of Events

Table 1: Schedule of Activities

Procedures	Screening Period (-60 Days to 0)	Baseline Visit (Study Day 1)	Week 4	Week 16	Week 28	Week 40	Week 52 ET/ED ³	Safety Follow-up ⁸
Informed Consent	X							
I/E Criteria	X	X						
Medical & Surgical History	X							
Adverse Events	X	X	X	X	X	X	X	X
Concomitant Meds	X	X	X	X	X	X	X	
Vital signs	X	X	X	X	X	X	X	
Physical Examination	X ¹	X	X	X	X	X	X	
Neurologic Examination	X ¹	X	X	X	X	X	X	
Height	X							
Weight	X	X	X	X	X	X	X	
Resting ECG	X	X ⁹	X		X		X	
Biochemistry, Hematology, Urinalysis	X	X	X	X	X	X	X	
Urine Drug Screen	X							
TSH, free T4, B12, HBsAg, HCV-Ab	X							
HbA1c (diabetic participants only)	X							

Procedures	Screening Period (-60 Days to 0)	Baseline Visit (Study Day 1)	Week 4	Week 16	Week 28	Week 40	Week 52 ET/ED ³	Safety Follow-up ⁸
Plasma P-tau181 or P-tau217	X ⁷							
Genotyping sample		X						
MRI	X							
PK and Plasma Biomarkers	X ²				X ²		X ²	
MMSE	X				X		X	
CDR	X						X	
Geriatric Depression Scale	X							
ADAS-Cog12		X	X	X	X	X	X	
ADCS-ADL		X	X	X	X	X	X	
NPI		X			X		X	
ZBI		X	X	X	X	X	X	
C-SSRS	X ⁴	X ⁵	X ⁵	X ⁵	X ⁵	X ⁵	X ⁵	
Drug Dispensation		X ⁶	X	X	X ⁶	X		
Drug Accountability			X	X	X	X	X	
End of Study Follow-up Phone Call								X

1. Complete Physical and Neurologic Examinations during the Screening Period only, brief examinations thereafter.
2. PK and plasma biomarker sub-study participants only (100 participants total; 50 participants/group).
3. Early Termination (ET) / Early Discontinuation (ED) participants do not need to complete the electronic clinical outcome assessments if performed within 30 days of the ET/ED Visit.
4. During the Screening Period, the C-SSRS baseline/Screening version will be administered.
5. At Study Day 1, as well as all remaining visits, the C-SSRS Since Last Visit version will be administered.
6. The first dose of Study Drug is administered at the clinic to all participants on Study Day 1; for plasma PK and biomarker sub-study participants only at the Week 28 visit, administer Study Drug after blood samples are collected.
7. Plasma P-tau181 or plasma P-tau217 not required if the participant has evidence for AD pathophysiology prior to screening.
8. This phone call will occur Week 53 to 54 for those participants who complete all study visits, or 1 to 2 weeks after ET. If the participant reports an adverse event, the participant should be followed and treated by the Investigator until the AE has resolved or stabilized.

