This study is considered a registration study. Statistical tests will be regarded as formal tests of specific hypotheses.

The data from nominal/scheduled protocol clinic visits will be included in visit-based summary tables. Unscheduled assessments, if they occur, and the ET visit data will be mapped to scheduled assessments according to the visit windows defined in section 6.1.5 for all safety and efficacy analyses. See Section 6.1.4 and 6.1.5 of this SAP for more details.

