14.2.7.2.3	ITT	Summary of Change from Baseline to Week 52 in NPI Total Score By Visit and Treatment Stratified by Mild (20-27)/Moderate (<20) AD Status : Responder Analysis
14.2.8.1	ITT	Summary of Change from Baseline to Week 52 in Zarit Burden Index By Visit and Treatment
14.2.8.2	ITT-mild	Summary of Change from Baseline to Week 52 in Zarit Burden Index By Visit and Treatment
14.2.9.1	ITT	Summary of Change from Baseline to Week 52 in P-tau 217 By Visit and Treatment
14.2.10.1	ITT	Summary of Change from Baseline to Week 52 in GFAP By Visit and Treatment
14.2.11.1	ITT	Summary of Change from Baseline to Week 52 in NfL by Visit and Treatment
14.2.12.1	ITT	Summary of Change from Baseline to Week 52 in Total Tau by Visit and Treatment

Table Number	Population	Table Title/Summary
14.2.13.1	ITT	Summary of Individuals Entering the Study with Mild (MMSE:21-27) Alzheimer's Disease (AD) and Progressed to Moderate (MMSE:16-20) or Severe (MMSE:<16) AD by Week 52
14.2.13.2	ITT	Summary of Individuals Entering the Study with Moderate (MMSE:16-20) Alzheimer's Disease and Progressed to Severe (Moderate:<16) AD by Week 52

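### Protocol Section 9 asks every early discontinuer for a plasma-biomarker draw that the schedule limits to the sub-study, and the SAP has no biomarker set to keep the extra samples out of the P-tau217 analysis

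*Protocol*

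**What the plan says.** All protocol references are to the current Version 3.0.

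- **Protocol Section 9 (Early Discontinuation).** The list opens with "The following must be completed and documented in the source documents and CRFs for all subjects who discontinue the study early". One entry is "Blood draw for plasma biomarkers", without qualification. The pointer to Section 7.1.6 in that list is attached to the rating scales, not to the blood draw.
- **Protocol 7.1.6 (Week 52 / Early Termination visit).** "For those 100 subjects participating in the PK and Plasma Biomarker sub-study, collect their Week 52 blood samples".
- **Protocol Appendix A, note 2**, which marks the Week 52 ET/ED cell: "PK and plasma biomarker sub-study subjects only (100 subjects total; 50 subjects/group". SAP Table 1 note 2 repeats it: "PK and plasma biomarker sub-study participants only (100 participants total; 50 participants/group".
- **Protocol 7.1.1 (Screening).** "Plasma for P-tau181 or P-tau217 assessment will also be collected unless there is documented evidence of AD pathophysiology prior to screening". People outside the sub-study can therefore have a screening P-tau value. Nothing comparable is planned for GFAP, NfL or total tau.
- **SAP 4.2.** For safety and efficacy analyses alike, "the ET visit data will be mapped to scheduled assessments according to the visit windows" set out in SAP 6.1.5.
- **SAP Table 6.** The only P-tau output is "Summary of Change from Baseline to Week 52 in P-tau 217 By Visit and Treatment", with ITT as its population. The GFAP, NfL and total tau tables are also set in ITT.
- **SAP Section 5.** ITT is all randomised participants. No biomarker set is defined. The PK sub-study set requires PK consent and a post-baseline PK value, and no biomarker table uses it.

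**The concern.** A site that follows Section 9 draws plasma from every early leaver; a site that follows the schedule draws only from sub-study members. The two instructions conflict.

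The statistical consequence is narrow. Outside the sub-study, a completer has no post-baseline biomarker sample. A dropout might have one, and if that person also has a screening value of the same P-tau species, a change score exists. With ITT as the population, a repeated-measures model on available data (SAP 8.3) and no biomarker set, nothing in the SAP keeps that score out. Entry into the comparison would then depend, for these people, on having discontinued, which happens after randomisation. If the reasons for stopping differ between arms, the P-tau217 contrast could be biased.

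For GFAP, NfL and total tau there is no mixing. Without a baseline the extra draws cannot give a change, so they are simply of no use to the planned analyses.

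**Working it through.** **Inputs.** Placebo change 5.0 points, SD 8.5, 45% difference, 90% power, two-sided 0.05, 20% dropout (Protocol 11.5, SAP 2.2). Planned N 750, final N 804 (SAP 2.2). Sub-study 100 (Appendix A note 2). Visit windows from SAP Table 2.1.

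**The plan's own figure.** Difference = 0.45 × 5.0 = 2.25. n per arm = 2 × (1.960 + 1.282)² × 8.5² / 2.25² ≈ 300, and 300 / 0.80 = 375. Both stated figures reproduce. The documents give no power or precision figure for the sub-study.

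**Draws outside the sub-study if Section 9 is followed.**
- N=750: 0.20 × (750 − 100) = 130
- N=804: 0.20 × (804 − 100) = 140.8, about 141

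This applies the 20% rate equally inside and outside the sub-study and supposes that every dropout attends an early-termination visit.

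**Share of Week 52 P-tau values.** Assume that dropout is uniform over Days 2 to 365 (364 days). Let f be the share of outside dropouts with a usable same-analyte baseline; the documents do not give it. The sub-study supplies 80 completers plus those of its own 20 dropouts whose sample maps to Week 52.

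*Nearest of the two biomarker visits, Weeks 28 and 52.* The midpoint of Days 197 and 365 is Day 281, so Days 282 to 365 map to Week 52: 84/364 = 0.231.
- Outside: 130 × 0.231 = 30.0; 140.8 × 0.231 = 32.5
- Sub-study: 80 + 20 × 0.231 = 84.6
- Share at f = 1: 30.0/114.6 = 26%; 32.5/117.1 = 28%

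*Table 2.1 windows, discarding samples in windows with no biomarker visit.* Days 324 to 365 map to Week 52: 42/364 = 0.115.
- Outside: 130 × 0.115 = 15.0; 140.8 × 0.115 = 16.2
- Sub-study: 80 + 20 × 0.115 = 82.3
- Share at f = 1: 15.0/97.3 = 15%; 16.2/98.5 = 16%

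*Smaller f, N=804:*

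| f | Nearest visit | Table 2.1 windows |
|---|---|---|
| 1 | 28% | 16% |
| 0.5 | 16.2/100.8 = 16% | 8.1/90.4 = 9% |
| 0.25 | 8.1/92.7 = 9% | 4.1/86.4 = 5% |
| 0 | 0% | 0% |

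At Week 28, the corresponding f = 1 counts from outside are 100 to 108 with nearest-visit mapping and 30 to 33 with the Table 2.1 windows, against at most 100 sub-study values.

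**What is known of f.** Entry criterion 5 and Protocol 7.1.1 allow P-tau181 or P-tau217 at screening, and neither is required where prior CSF or PET evidence exists. Protocol 7.2.1 describes the P-tau181 assay as validated and the P-tau217 validation as pending. The only P-tau table is for P-tau217. The documents set no lower limit on f.

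**With Section 9 limited to the sub-study.** Contributors are at most the 100 planned participants (about 80 completers and 20 dropouts), with none from outside.

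**The case against.** The strongest case against the point is that Section 9 merely lacks a qualifier that three other places supply. Sample preparation (Protocol 7.2.3) is described only for sub-study participants, so sites may well have read it that way. The draw counts are ceilings: SAP 7.1 expects some loss to follow-up, and SAP 8.1.1 records four deaths. SAP 6.1.5 also has a rule that drops early-termination assessments falling where that assessment is not scheduled. All of this bears on the size. None of it removes the contradiction or supplies a biomarker set. The window rule stands with the safety windows, while the efficacy paragraph speaks only of the nearest scheduled visit, so its reach is uncertain.

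Three stronger readings are tempting, and the documents do not support them.

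- A reader might set 141 outside dropouts against 100 planned participants and infer that dropouts from outside make up more than half of the P-tau sample. That count takes in anyone contributing at any visit and needs a P-tau217 baseline for every one of them, which the screening rules do not provide.
- A reader might infer from the 4.5 to 6 hour half-life (Protocol 2.3) that early-termination samples are contaminated by being off drug. That half-life is simufilam's in healthy volunteers; nothing says P-tau reverts on that scale. The SAP also handles dosing deviations by treatment policy, for exploratory endpoints too (SAP 3.2.1.3).
- A reader might infer harm to the trial's main conclusions. Biomarkers are outside the testing hierarchy (SAP 6.1.3), tertiary in SAP 3.2.1.3 and destined for a separate report. Protocol Section 4 and SAP 2.1 do call them additional secondary endpoints, but no co-primary or hierarchy-controlled test uses them.

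**Conclusion.** The point holds as a minor internal inconsistency. Section 9 conflicts with Section 7.1.6, Appendix A and SAP Table 1. Followed as written, it would lead to as many as 130 to 141 draws that the schedule excludes. The SAP, with its biomarker outputs in ITT, would let any of these people who have a same-analyte screening value into the P-tau217 comparison.

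The size of that mixing is unknown. At Week 52 it is at most about 28% with nearest-visit mapping or about 16% with the unscheduled-window rule, and it could be near zero. Those upper figures rest on 20% dropout at the same rate in and out of the sub-study, uniform timing, full attendance at early-termination visits and a usable baseline for all; later dropout would raise them. Bias is possible but not shown, since it requires reasons for stopping that differ by arm. Co-primary inference is unaffected.

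**What to change.** **Protocol Section 9.** Add *(sub-study participants only)* to the plasma-biomarker item, so that it agrees with Section 7.1.6 and Appendix A.

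**SAP Section 5 and Tables 6 and 9.** Define a biomarker sub-study set: randomised sub-study participants with a baseline sample, analysed as randomised. Use it in place of ITT for the P-tau217, GFAP, NfL and total tau outputs. Sub-study dropouts' early-termination samples are kept.

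**SAP 6.1.5.** State whether the rule on windows without a scheduled assessment applies to early-termination biomarker samples.

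The cost is one protocol qualifier, one analysis-set definition and one sentence on windows. No planned data are lost. The SAP changes should be made before unblinding so that they count as prespecified. Even if the Section 9 edit comes too late to prevent draws, the analysis set keeps outside samples out of the comparison. An added PK sample or time of last dose is not needed to settle this point.

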10. ADVERSE EVENTS/SERIOUS ADVERSE EVENTS

10.1. ADVERSE EVENTS - DEFINITION

An Adverse Event (AE) is any undesirable event that occurs to a subject during a study, whether or not that event is considered related to Study Drug. Monitoring for AEs will start after informed consent has been obtained. Examples include:

- Any treatment-emergent signs and symptoms (events that are marked by a change from the subject's baseline/entry status [e.g., an increase in severity or frequency of pre-existing abnormality or disorder])
- All reactions from Study Drug, an overdose, abuse of drug, withdrawal phenomena, sensitivity or toxicity to Study Drug
- Apparently unrelated illnesses
- Injury or accidents (Note: if a medical condition is known to have caused the injury or accident, the medical condition and the accident should be reported as two separate medical events [e.g., for a fall secondary to dizziness, both "dizziness" and "fall" should be recorded separately])
- Extensions or exacerbations of symptoms, subjective subject-reported events, new clinically significant abnormalities in clinical laboratory, physiological testing or physical examination

All AEs, whether or not related to Study Drug, must be fully documented on the AE page of the CRF and in the subject's clinical chart. Adverse events reported during the screening period or AEs secondary to study-related procedures should always be captured as not having a reasonable possibility the AE was caused by the Study Drug. Unexpected, abnormal laboratory results observed during the Screening Period should be captured as Medical History and not as an AE.

In the event that a subject is withdrawn from the study because of an AE, it must be recorded on the CRF as such. The subject should be followed and treated by the Investigator until the abnormal parameter or symptom has resolved or stabilized.

The Investigator must report all directly observed AEs and all spontaneously reported AEs. The Investigator will ask the subject a non-specific question (e.g., "Have you noticed anything different since your dose of the study medication?") to assess whether any AEs have been experienced since the last assessment. AEs will be identified and documented in the Electronic Data Capture (EDC) system in appropriate medical terminology. The severity and the relationship to the Study Drug will be determined and reported in EDC (see below).

